7.2.1 Primary Safety Endpoint(s)

[figure not shown]
Not applicable.

7.2.2 Secondary Safety Endpoints

Incidences of related TEAEs will be provided by system organ class (SOC) and preferred term (PT).

[figure not shown]
7.4 Special Statistical/Analytical Issues

[figure not shown]
7.4.1 Discontinuations and Missing Data

Multiple imputation (MI)

Missing post-baseline data for the primary endpoint will be replaced by multiple imputation. Multiple imputations will only be performed for subjects with a missing MAS ‘Décolleté Wrinkles – At Rest’ score at 16 weeks after last treatment who did not discontinue before 16 weeks after last treatment due to lack of effectiveness. Subjects who will discontinue due to the reason given above will be treated as non-responders.

All further specifications for MI are based on the assumption that the MAS ‘Décolleté Wrinkles – At Rest’ assessment at 16 weeks after last treatment is missing at random, i.e.; being missing will not depend on the MAS at 16 weeks after last treatment itself but will only depend on the factors in the imputation model.

[figure not shown]

[figure not shown]
Last observation carried forward (LOCF)

For secondary effectiveness endpoints, missing values will be replaced by the last available value before 16 weeks after last treatment.

Observed cases (OC)

For the OC method, no missing value imputations will be conducted. All data will be analyzed as observed. This method will be used [REDACTED] to assess the sensitivity of the MI and the LOCF method for primary and secondary effectiveness endpoints.

7.4.2 *Interim Analyses*

Not applicable.

7.4.3 *Data Monitoring Committee*

[figure not shown]
Not applicable.

7.4.4 *Multiple Comparisons/Multiplicity*

[REDACTED] the type one error rate has not to be adjusted.

7.4.5 *Examination of Subgroups*

[figure not shown]

The supportive exploratory analyses for the primary effectiveness endpoint will also be performed for the observed cases in the FAS (i.e. on randomized treatment groups).

A further subgroup analysis for the following safety endpoints will be presented for the subgroup of subjects that had three injections with a cannula:

- Adverse events: Incidences of TEAEs, non-serious TEAEs and serious TEAEs will be provided by SOC and PT. Incidences of TEAEs will be provided overall and by worst intensity, by worst outcome, and by treatment area affected (yes/no). Treatment-related TEAEs will be presented by injection cycle.

[figure not shown]

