3.3.2 Informed Consent

Informed consent will be obtained in accordance with EN ISO 14155:2011 (chap. 4.7) in writing directly from the subject.

The consent must be confirmed by the investigator (or authorized designee) who conducted the informed consent briefings. The informed consent process must be traceable from the available documentation. At a minimum, this documentation should include information about when the subject was first informed about the investigation and who supplied the information. The subject will be given a copy of the signed and dated written informed consent form as well as all consent form updates (if applicable).

During the course of the investigation, the subject has to be informed in a timely manner if information becomes available that may be relevant to the subject's willingness to continue participation in the investigation. In case of AEs, or poor tolerability to the IMD, the subject should inform the investigator, who then will make a judgment whether continuing in the investigation serves the subject's best interests. The subject, however, is free to withdraw consent at any time and for any reason, whether expressed or not.

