7.4 Removal of Subjects from Treatment or Assessment

7.4.1 Discontinuation of Subjects

In accordance with the Declaration of Helsinki and the informed consent form, the subject may discontinue the investigation at any time without any penalty or loss of benefits to which the subject is otherwise entitled (see Section 7.4.3). Premature discontinuation of the investigation with its reason(s) must be recorded in the subject file and the eCRF. Date and discontinuation circumstances should be stated.

Subjects must be discontinued from the investigation by the investigator at any time for any of the following reasons:

• Withdrawal of informed consent.

- Pregnancy (no further injection of IMD, or any other interventional procedure will be performed).
- Any AEs for which treatment continuation would constitute an unacceptably high risk for the subject.

CIP deviations or conditions arising from the exclusion criteria established in Section 7.3, may lead to the subject's discontinuation. All such conditions should be properly documented.

Subjects who are discontinued from the investigation due to AEs will be treated according to standard clinical strategies and will be followed-up until the final investigational visit/safety visit. All pertinent information concerning the AE will be documented in the subject file as well as in the eCRF AE report form.

Following discontinuation, a final examination should be performed for safety reasons. The investigator is required to make every effort to contact subjects lost to follow-up, and all such efforts should be documented in the subject file (e.g., times and dates of telephone contact, copies of letters).

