9.2.5 Treatment Satisfaction Assessments

9.2.5.1 Subject's Treatment Satisfaction Assessment

Subjects will be queried on the level of subject treatment satisfaction (see Appendix 16.4) with the IMD treatment by being asked: "How satisfied or dissatisfied are you with the aesthetic appearance of your décolleté today? Please tick the one option that best fits."

If the subject responds "somewhat dissatisfied", "dissatisfied", or "very dissatisfied", he/she will be asked for additional explanation as to why he/she is not satisfied. Additional explanation, if any, will be kept within the source data and entered at a separate (from the scale) comment field on the eCRF.

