12.1 Determination of Sample Size

The primary effectiveness endpoint is the proportion of subjects with at least 1 point (≥ 1 point) improvement on the MAS Décolleté Wrinkles-At Rest scale at 16 weeks after last treatment compared to baseline (Day 1)

. By use of a one-sided binomial test, it will be tested at an error level of 2.5% whether the response rate is significantly larger than 50%. It is aimed to ensure a power of 90%. The binomial test is applied to the pooled data from both treatment groups.

To account for up to 10% drop-outs and potential exclusions from the FAS, a total of 112 subjects need to be enrolled in this study, i.e., 56 subjects need to be randomized to each treatment group.

Per definition, the SES will be at least as large as the FAS. Thus, according to the above outlined assumptions, at least 100 subjects will be available for safety analyses. This sample size is sufficient to observe, with a probability of 80%, at least one adverse event with actual event probability of 1.6%.

With regard to safety analyses, it should be considered that the RADIESSE[®] in its original un-diluted form is marketed since 2003. Since then, over 5 million units had been sold and used in a variety of subject populations. In this period, the majority of reported AEs were common expected injection site reactions that were mild in nature and resolved over time.

Consequently, the sample size for this study was primarily determined to ensure an adequate power for the primary effectiveness analysis, however, still providing a good probability of risk detection.

Calculations to determine the required sample size were performed using the software nQuery Version 8.1.2.0, Statistical Solutions Ltd. 2017, and validated by double programming with proc power on SAS 9.4, SAS Institute Inc., Cary, NC, USA, 2016.

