4 DETERMINATION OF SAMPLE SIZE

The primary effectiveness endpoint is the proportion of subjects with at least 1 point (≥ 1 point) improvement on the MAS Décolleté Wrinkles – At Rest scale at 16 weeks after last treatment compared to baseline (Day 1). [REDACTED]. By use of a one-sided binomial test, it will be tested at an error level of 2.5% whether the response rate is significantly larger than 50%. It is aimed to ensure a power of 90%. The binomial test is applied to the pooled data from both treatment groups. [REDACTED]

Per definition, the safety evaluation set (SES) will be at least as large as the FAS. Thus, according to the above outlined assumptions, at least 100 subjects are planned to be available for safety analyses. This sample size is sufficient to observe, with a probability of 80%, at least one adverse event with actual event probability of 1.6%.

With regard to safety analyses, it should be considered that the RADIÉSSE® in its original undiluted form is marketed since 2003. Since then, over 5 million units had been sold and used in a variety of subject populations. In this period, the majority of reported AEs were common expected injection site reactions that were mild in nature and resolved over time. [REDACTED]

[REDACTED] The large extent of the exposure to the undiluted RADIÉSSE® worldwide versus the relatively small number of complications led to the conclusion that its safety has already been established to a sufficient degree. As it is not expected that dilution of RADIÉSSE® Volume Advantage 1.5 mL Injectable Implant with saline will cause more AEs, it is assumed the safety can be transferred to the IMD.

Consequently, the sample size for this study was primarily determined to ensure an adequate power for the primary effectiveness analysis, however, still providing a good probability of risk detection.

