7 STATISTICAL ANALYSIS METHODS

In the following, the term “treatment group” refers to the realized treatment group. This may differ from the randomized treatment group as those subjects randomized to group A [REDACTED] who did not manage to get their second injection in due time due to the COVID-19 public health emergency measures were allowed to skip this treatment and proceed with the last foreseen treatment. By this measure, these subjects switched to treatment group B [REDACTED]. Assuming that the mechanism of being prevented from performing the second treatment visit due to COVID-19 public health emergency measures is independent from any known or unknown, potentially confounding factors, the realized treatment groups should still be comparable in their baseline characteristics and analyses on them of high scientific value.

In the sections below, baseline severity refers to the severity of wrinkles on the MAS ‘Décolleté Wrinkles – At Rest’ as assessed [REDACTED].

For all analyses concerning ‘16 weeks after last treatment’, assessments of the visit closest to 16 weeks after last treatment within the time frame of 12 to 20 weeks after last treatment will be used. In case no visit was performed in the specific time frame, the assessments for ‘16 weeks after last treatment’ will be treated as missing.

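### The non-responder rule for lack-of-effectiveness discontinuation ends at 16 weeks after last treatment, while the assessment window it serves runs to 20 weeks

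*SAP*

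**What the plan says.** The primary endpoint is response on the MAS Décolleté Wrinkles-At Rest, meaning an improvement of at least one point from baseline to 16 weeks after last treatment. The two groups are pooled and compared with a fixed rate; in SAP section 4, "it will be tested at an error level of 2.5% whether the response rate is significantly larger than 50"%.

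Two rules decide how a subject enters that test.

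- **Assessment window (SAP section 7).** For every 16-week analysis the closest visit "within the time frame of 12 to 20 weeks after last treatment will be used". With no visit in that window, the value is missing.
- **Missing scores (SAP section 7.4.1).** Multiple imputation applies only to subjects with a missing score "who did not discontinue before 16 weeks after last treatment due to lack of effectiveness". Subjects who did discontinue for that reason are non-responders. All other missing scores are imputed under missing at random and, by SAP section 7.1.1, within each realized treatment group.

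On reasons for leaving, Protocol section 3.3.2 says that the subject is "free to withdraw consent at any time and for any reason, whether expressed or not". Protocol section 7.4.1 requires the reason for premature discontinuation to be recorded in the subject file and the eCRF.

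**The concern.** The two time limits do not match. The score may be obtained until week 20, but the clause that turns a lack-of-effectiveness leaver into a failure stops at week 16. Between those limits a subject who has not been seen can leave because the treatment failed and still fall under missing at random. By making known lack-of-effectiveness leavers non-responders, the SAP accepts that their missing score depends on outcome. Nothing visible explains why this should cease at week 16.

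The design makes any such credit count in full. The test has one pooled sample and a fixed 50% reference, so no comparator arm carries a similar error that could cancel it. The visible sensitivity analyses of the primary endpoint use observed cases, in the modified FAS and in the PPS. They drop such a subject and would not show her as a failure. Late visits are plausible, because SAP section 3.1 reports that visit windows were widened and later visits moved on account of COVID-19.

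**Working it through.** **Step 1. The two rules side by side.** Take subjects with no visit from week 12 up to the time they leave, no MAS score at exit, and lack of effectiveness recorded as the reason.

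| Leaves at | In-window score | Discontinued before week 16 | Handling in primary analysis |
|---|---|---|---|
| week 15 | none | yes | non-responder |
| week 17 | none | no | multiply imputed |

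The only difference is the date of leaving. A score at any visit in weeks 12 to 20 would be used as observed in either case.

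**Step 2. The plan's own sample size.** Protocol section 12.1 enrols 112 subjects "To account for up to 10% drop-outs and potential exclusions from the FAS". From 100 evaluable subjects, 100 / (1 − 0.10) = 111.1, rounded up to 112, which reproduces. The 90% power cannot be reproduced because the assumed response rate is blacked out. Working backwards, an exact one-sided 2.5% test with n = 100 rejects at 61 or more responders and needs a true rate of 66.6% for 90% power. That is the reason for taking 0.6 to 0.7 below as the imputed probability for an average subject. It is an assumption.

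**Step 3. Credit per subject.** If k true failures are imputed with response probability p instead of being set to zero, the pooled rate rises by 100 × k × p / 112 percentage points.

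| p | k = 1 | k = 3 | k = 6 |
|---|---|---|---|
| 0.2 | 0.18 | 0.54 | 1.07 |
| 0.6 | 0.54 | 1.61 | 3.21 |
| 0.7 | 0.62 | 1.88 | 3.75 |

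The row p = 0.2 illustrates an imputation model that uses a poor early course. The number k is not in the documents.

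**Step 4. Effect on the test, conditional on k.** Let the true overall rate be exactly 50% of 112, that is 56 responders on average, with k failures imputed at the average rate. As an observed-case approximation, n = 112 − k and the rate among the rest is q = 56 / n. The exact cut-off is the smallest count with null probability below 2.5%.

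| k | n | q | cut-off | chance of rejecting |
|---|---|---|---|---|
| 0 | 112 | 50.0% | 67 | 2.3% |
| 1 | 111 | 50.5% | 67 | 2.3% |
| 3 | 109 | 51.4% | 66 | 3.4% |
| 6 | 106 | 52.8% | 64 | 7.2% |

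A simulation of the imputation itself gives the same picture. It used 20,000 trials, 12 of 112 scores missing (assumed), an imputation model without covariates, 50 imputations and Rubin's rules. Rejection was 2.9% at k = 0, 3.2% at k = 1, 4.9% at k = 3 and 8.8% at k = 6. With the k subjects set to non-response, it was 2.5%, 2.4% and 2.6% at k = 1, 3 and 6.

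**The case against.** **The gap is narrow, and perhaps only one of wording.** It needs a subject with no visit from week 12 who leaves at weeks 16 to 20, gives lack of effectiveness as the reason, and has no MAS score at exit. Protocol sections 7.4.1 and 9.5 provide for a final examination or assessment after discontinuation. If MAS is scored there, which the visible text does not say, the window would capture it. SAP section 7 also defines the 16-week assessment for all analyses, so the clause may have been meant as before the windowed assessment. All of this stands as a limit on size. It does not remove the literal conflict, and a rule for the primary analysis should not depend on the reader guessing the intent.

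**The imputation model is not visible.** SAP section 7.4.6 speaks of regression models with site as a factor, and Protocol section 12.4.4.1 ties imputation to the reasons for missingness before its visible text ends. If earlier MAS scores enter the model, the credit shrinks. This stands, and the values at 0.6 to 0.7 are therefore upper-end.

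**A stronger reading is tempting.** A reader might infer that dissatisfied leavers in general are imputed as partial responders, because consent can be withdrawn without a reason and "Withdrawal of informed consent" heads the visible list of mandatory discontinuation reasons. The documents do not support that. Subjects recorded as leaving for lack of effectiveness before week 16 are already failures. The list states when the investigator must discontinue a subject; it is not the set of reasons offered in the eCRF. The same section requires reasons to be recorded. When a subject reports dissatisfaction, "he/she will be asked for additional explanation as to why he/she is not satisfied". How an unexplained withdrawal would be classified is not stated, so dependence on the recorded reason is a limitation to note and no more.

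**Conclusion.** The mismatch holds on the literal text: the non-responder rule ends four weeks before the window closes. Its effect is small, at most about 0.5 to 0.6 percentage points per affected subject at an assumed imputed probability of 0.6 to 0.7, and less if the model uses earlier scores. The number affected is unknown.

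A reader might also infer that the type I error is inflated to 3.4% or 7.2%. Those figures apply only if 3 or 6 uncaught failures are imputed at the average rate. Six would be about half of the 11 to 12 subjects implied by a 10% loss from 112, and one such subject leaves the exact calculation at 2.3%. The week 16 to 20 gap alone gives no ground for expecting that many. The figures show how the test would respond; they do not predict its error rate.

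**What to change.** In SAP section 7.4.1, replace the limit of 16 weeks after last treatment by a limit tied to the window: discontinuation for lack of effectiveness before an in-window assessment, up to 20 weeks after last treatment. Any subject without a score at 12 to 20 weeks who discontinued for that reason by week 20 is then a non-responder, and multiple imputation applies to the remaining missing scores.

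Add a sentence acknowledging that the rule relies on the recorded reason and that a subject may leave without giving one.

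Do not reclassify subjects automatically in the primary analysis from their last satisfaction or sGAIS rating. That would set a blinded-rater outcome to failure from an unblinded subject's rating on another scale. By Protocol section 6.1 the questionnaires are also completed at injection visits, before injection, so the last rating may predate the final treatment. A subject who left because of COVID-19 could be failed in error.

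The cost is one amended clause and one added sentence, with no new data. The downside is a slightly lower estimated response rate.

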8.2.6 Treatment of Overdose

As treatment with the IMD is performed exclusively in a clinical setting under the supervision of trained medical personnel, the risk of overdose in this investigation is estimated to be low.

However, in the case an overdose occurred (i.e., over-correction), it must be recorded in the source documents and the IMD section of the eCRF and recorded as an AE. Any case of overdose leading to a SAE(s) must be reported to the sponsor in an expedited manner using the appropriate reporting form (see Section 10). Usually, overcorrection is an aesthetic issue and harmless for health. It resolves within six to 12 months without intervention. For the IMD used in this investigation, no antidote has been identified to date, and there is no known established therapy recommended for an overcorrection. The investigator is advised to use best clinical judgment in the unlikely event of an overcorrection with the IMD. Kadouch et al. [Kadouch 2017] recommend treating nodules resulting from overcorrection with massaging, aspiration, intralesional injection with sterile water or corticosteroids.

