8.3 Previous and Concomitant Therapies/Procedures

After signature of informed consent and prior to randomization, the subject's medical history should include a detailed list of all medications (including rescue medication) and over-the-counter or prescription, oral or topical, anti-wrinkle or skin enhancer products (e.g., alpha hydroxyl acids, glycolic acids, skin-bleaching agents, retinol, or retinoic acids in the décolleté) the subject was taking for a period of at least 3 months previous to randomization. The record should include the drug name (trade or generic), route of administration (e.g., intravenous, oral), total daily dose/unit (expressed in mg, mL, or International Unit [IU]), indication, the start and stop date (day, month, and year) for each medication, and if the medication is ongoing at the end of the investigation.

Similar information should be collected and assessed for any non-drug therapies that may have an impact on investigational results, e.g., dermal treatments in the décolleté such as toxin treatments, ablative or fractional laser, microdermabrasion, microneedling, chemical peels, non-invasive skin tightening, implantation of non-permanent or permanent dermal fillers, surgical procedures (including implantation of ports, pacemakers or defibrillators and breast augmentation), regardless of time point before randomization.

The medical history including relevant non-drug therapies (as defined in the prior paragraph) have to be documented in the source documentation and the eCRF.

Local anesthetics, sedation or cooling applied prior to or after injection should be documented (please refer to the Section 8.1.3).

The following concomitant medications are forbidden during the investigation:

• During the whole course of the investigation:

• For ten days prior to and three days after treatment (applies to all injection cycles):

The following concomitant non-drug treatments are forbidden during the investigation:

• During the whole course of the investigation:

• For at least 24 hours after treatment (applies to all injection cycles):

• For at least 12 hours after treatment (applies to all injection cycles):

• At the day of a visit before assessments (applies to all visits):

Concomitant medication and concomitant non-drug treatments have to be documented in the source documentation and in the eCRF. This also applies to therapy changes (including changes of regimen) during the investigation.

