7.1.1 Primary Effectiveness Endpoint(s)

The primary effectiveness endpoint is the proportion of responders (responder rate) defined as subjects with ≥ 1 -point improvement on the MAS 'Décolleté Wrinkles – At Rest' from baseline to 16 weeks after last treatment as assessed [REDACTED].

The primary analysis will be based on a one-sided binomial test at the one-sided type I error level of $\alpha = 0.025$ for the pooled data from both treatments against the null-hypothesis that the response rate (R) is $\leq 50\%$:

$$H_0 : R \leq 50\%$$

$$H_1 : R > 50\%.$$

H_0 is rejected if the resulting one-sided p-value is <0.025 and the observed proportion of responders is >0.5 .

As further supportive explorative analyses, the effectiveness for the different time points of treatments with a 16 weeks post-treatment period in both treatment groups will be analyzed as for the primary endpoint:

- Proportion of responders (response rate) defined as subjects with ≥ 1 -point improvement on the 'MAS Décolleté Wrinkles – At Rest' from last treatment application to 16 weeks after last treatment as assessed [REDACTED].
- Proportion of responders (response rate) defined as subjects with ≥ 1 -point improvement on the MAS 'Décolleté Wrinkles – At Rest' from last treatment application to 16 weeks after last treatment as assessed [REDACTED].
- Proportion of responders (response rate) defined as subjects with ≥ 1 -point improvement on the MAS 'Décolleté Wrinkles – At Rest' from baseline to 16 weeks after first treatment as assessed [REDACTED].

In addition, two-sided 95% Wilson score confidence intervals for response rates will be provided overall, and for each treatment group in the supportive analyses. A similar SAS code as given above will be used.

The primary effectiveness analyses will be based on the modified FAS with missing data replaced by a multiple imputation approach for each realized treatment group.

Sensitivity analyses of the primary endpoint will be provided based on observed cases only in the modified FAS and on the observed cases in the PPS. The supportive explorative analyses will be performed on the observed cases in the modified FAS as well as on observed cases in the FAS. For analysis based on observed data, SAS code similar to the following will be used:

```
proc freq data = dataset order = freq;  
  tables response / binomial (level="1" wilson p=.5) cl alpha=.05;  
run;
```

, assuming the response is coded with '1' and no response is coded with '0'.

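### On the visible text, a subject whose wrinkles improve after another décolleté procedure before the 16-week rating can count as an MRZF111 responder in the primary uncontrolled test against 50%

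*SAP*

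**What the plan says.** **Endpoint and test.** Response is an improvement of at least 1 point on MAS Décolleté Wrinkles-At Rest from baseline to 16 weeks after last treatment (Protocol 12.3.1.1, SAP 6.1.1). The visible definition sets no condition on other procedures. Both regimens are pooled and compared with a fixed rate: the question is "whether the response rate is significantly larger than 50"% (Protocol 12.1). In SAP 7.1.1, "The primary analysis will be based on a one-sided binomial test at the one-sided type I error level of" 0.025, and the null hypothesis "is rejected if the resulting one-sided p-value is <0.025 and the observed proportion of responders is >0.5". Protocol 6.2 states that there is no control group.

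**Which rating counts.** SAP 7 uses "assessments of the visit closest to 16 weeks after last treatment within the time frame of 12 to 20 weeks" after last treatment. The rating is missing only if no visit falls in that window.

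**Missing ratings.** SAP 7.4.1 imputes missing At Rest scores under missing at random, except after discontinuation for lack of effectiveness: "Subjects who will discontinue due to the reason given above will be treated as non-responders".

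**Other procedures.** Protocol 8.3 says: "The following concomitant non-drug treatments are forbidden during the investigation". One heading covers the whole course of the investigation; others cover short periods after injection and the day of a visit. The items are blacked out. The same section names toxin, ablative or fractional laser, microdermabrasion, microneedling, peels, skin tightening, fillers and surgery as therapies that may influence results, and requires concomitant non-drug treatments to be entered in the eCRF. Under Protocol 7.4.1, "CIP deviations or conditions arising from the exclusion criteria established in Section 7.3, may lead to" discontinuation, so withdrawal is not automatic.

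**Analysis sets.** The primary set is the modified FAS, which requires exposure and a baseline score. The PPS removes major deviations but serves as a sensitivity analysis (SAP 5, 7.1).

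**The concern.** The plan treats leaving for lack of effectiveness as a failure. A subject who is not satisfied and has something else done to the same skin is a failure of the same kind, yet the visible rule depends on the recorded reason for discontinuation and does not reach her if she stays in the study.

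The single-rate design makes this matter. With no untreated arm, nothing separates improvement due to MRZF111 from improvement due to an added procedure. Comparing groups A and B does not help, since both receive the device. Blinding the rater to the regimen does not help either, because the rater scores the skin as it looks. Subjects who have not improved are plausibly the likeliest to seek another procedure, so the error would mostly turn non-responders into responders.

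**Working it through.** **1. Following one subject through the visible rules.** She has a result-affecting décolleté procedure after first injection and before the 16-week rating.

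| Situation | Rule | Primary outcome |
|---|---|---|
| Rated at 12-20 weeks | SAP 7 | Score used as observed |
| No rating; discontinued for lack of effectiveness | SAP 7.4.1 | Non-responder |
| No rating; any other reason | SAP 7.4.1 | Imputed under missing at random |

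She can be a responder in the first and third rows. No visible text on the modified FAS, the endpoint or missing data changes that.

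**2. The plan's own figures.** 100/0.9 = 111.1, rounded up to 112, which matches the stated enrolment. 1 - (1 - 0.016)^100 = 0.801, which matches the stated 80% chance of seeing an event of probability 1.6%. The 90% power cannot be checked because the assumed response rate is not visible. None of these figures is in dispute.

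**3. Cut-offs.** The smallest k with P(X ≥ k | n, 0.5) < 0.025, exact binomial:

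- n = 100: k = 61 (p = 0.0176; 60 gives 0.0284).
- n = 112: k = 67 (p = 0.0234; 66 gives 0.0361).

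At the margin, one subject decides the result.

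**4. Illustration.** Assumptions, since the documents give no frequencies: the true rate is 50%, a share f of non-responders has a procedure, and a share q of those is then rated a responder. The counted rate is p = 0.5 + 0.5 × f × q, and the chance of a false success is P(X ≥ k | n, p).

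| f | q | p | n = 100 (k = 61) | n = 112 (k = 67) |
|---|---|---|---|---|
| 0 | – | 0.500 | 1.8% | 2.3% |
| 2% | 50% | 0.505 | 2.2% | 3.0% |
| 5% | 50% | 0.5125 | 3.2% | 4.2% |
| 5% | 80% | 0.520 | 4.4% | 5.9% |
| 10% | 50% | 0.525 | 5.4% | 7.2% |
| 10% | 80% | 0.540 | 9.6% | 12.7% |

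The expected number of reclassified subjects in the 5%-10% rows is n × 0.5 × f × q: 1.25 to 4.0 at n = 100, and 1.4 to 4.5 at n = 112.

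**5. Power cost of the stricter rule.** At n = 100, 90% power corresponds to a true rate of about 0.666 (back-solved, not a figure from the plan). If the rule moves 2% of all subjects from responder to non-responder, the rate is 0.646 and power about 80%. At 5% it is 0.616 and about 59%.

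**6. Limits of the arithmetic.** The primary test will combine multiply imputed data, so it is not exactly this binomial. A normal-approximation test would cut at 60 of 100 and at 67 of 112.

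**The case against.** **Hidden text.** SAP 6.1.1 and 7.4.1 have redactions or missing figures, and Protocol 12.4.4.1 breaks off after saying that imputation depends on the reason for missingness. A reader might infer that the plan as a whole contains no other non-response rule. The documents do not support that; only the visible text can be judged. The visible parts of 12.4.4.1 and 7.4.1 do concern missing data, however, whereas the main gap is an observed score after a procedure.

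**The forbidden list.** Its items are blacked out. The procedure types named here come from the history-taking paragraph of Protocol 8.3, so which of them are forbidden is not confirmed.

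**Discontinued subjects.** A dissatisfied subject may have lack of effectiveness recorded as her reason, and then the existing rule covers her. Nor can one say that imputation would draw only on other subjects: the model is not visible and may use her own earlier scores. She can be imputed as a responder; it is not shown that she would be.

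**Corrective treatment.** Protocol 8.2.6 cites a safety review said to "recommend treating nodules resulting from overcorrection with massaging, aspiration, intralesional injection with sterile water or corticosteroids". A reader might infer that ratings after such measures also inflate the response rate. Nothing in the documents shows that they improve the wrinkle grade, and counting them as failures would put a safety event into an effectiveness endpoint. That extension is not supported.

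**The PPS.** It is a prespecified check, with exclusions fixed before database lock, and may remove these subjects. It leaves the primary result unchanged, its visible text does not name such procedures as major deviations, and it drops the subjects instead of counting them as failures.

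**Rarity.** With 2% uptake, half improving and 100 subjects, the error stays below 2.5%. That is fair, and is why the number of such subjects should be reported.

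**Conclusion.** The concern holds for the visible text and for procedures that can themselves improve décolleté wrinkles: followed as written, the rules allow such a subject to count as a responder in the primary analysis. If a rule in the unseen parts already covers this, the point falls away.

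The size is illustrative. In the 5%-10% uptake scenarios the false-success probability is 3.2% to 9.6% at the 100 evaluable subjects planned, and 4.2% to 12.7% if all 112 enrolled are counted. A reader might take the upper values as an estimate of actual error; they are not, because uptake and success after a procedure are both assumed. The direction rests on the further assumption that procedures are sought mainly by subjects who have not improved.

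Counting these subjects as non-responders is one estimand choice, but it is consistent with the plan's own treatment of lack of effectiveness. The point should be settled before database lock.

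**What to change.** 1. In SAP 7.4.1, for the primary modified FAS analysis of MAS At Rest, count as a non-responder any subject with a recorded décolleté procedure, between first injection and the 16-week rating, that is forbidden for the whole course of the investigation and can affect the wrinkle rating. Apply this whether or not a score exists and whatever the discontinuation reason.
2. State what is not included: the short peri-injection and visit-day restrictions, massage (which Protocol 8.1.3 permits after injection) and corrective treatment of adverse events.
3. State the same rule separately for MAS Dynamic. The visible non-responder rule is written for At Rest, and missing secondary values are handled by LOCF.
4. Identify these subjects from the eCRF concomitant non-drug treatment data before database lock, and report their number.
5. Keep the current handling (score as observed, or imputed if missing) as a sensitivity analysis.
6. If a rule in the text not visible here already covers this, refer to it in SAP 7.4.1 instead.

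The cost is a few lines of SAP text and one derivation from data already collected, with a slightly lower response rate and some loss of power. The rule concerns only how outcomes are counted, not which procedures are acceptable.
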